3.5. Multiple Comparisons

Not applicable.

3.6. Missing Data and Outliers

3.6.1. Missing Data

In general, missing data will not be imputed unless methods for handling missing data are specified. Exceptions are presented in this document.

For missing last dosing date of study drug, imputation rules are described in Section 4.2.1. The handling of missing or incomplete dates for disease diagnosis is described in Section 5.3, for SCT and new anticancer therapy in Section 6.1.2, for death in Section 6.2.2, for AE onset in Section 7.1.5.2, and for prior and concomitant medications in Section 7.4.

3.6.2. Outliers

Outliers will be identified during the data management and data analysis process, but no sensitivity analyses will be conducted. All data will be included in the data analysis.

3.7. Data Handling Conventions and Transformations

The following conventions will be used for the imputation of date of birth when it is partially missing or not collected:

- If only month and year of birth is collected, then “15” will be imputed as the day of birth
- If only year of birth is collected, then “01 July” will be imputed as the day and month of birth
- If year of birth is missing, then date of birth will not be imputed

In general, age collected at Day 1 (the first dosing date of study drug) (in years) will be used for analyses and presented in listings. If age at Day 1 is not available for a subject, then age derived based on date of birth and the Day 1 visit date will be used instead. If an enrolled subject was not dosed with any study drug, the randomization or enrollment date will be used instead of the Day 1 visit date. For screen failures, the date the first informed consent was signed will be used for the age derivation. Age required for longitudinal and temporal calculations and analyses (eg, estimates of creatinine clearance, age at date of AE) will be based on age derived from date of birth and the date of the measurement or event, unless otherwise specified.

Non-PK data that are continuous in nature but are less than the lower limit of quantitation (LOQ) or above the upper LOQ will be imputed as follows:

- A value that is 1 unit less than the LOQ will be used to calculate descriptive statistics if the datum is reported in the form of “< x” (where x is considered the LOQ). For example, if the values are reported as < 50 and < 5.0, values of 49 and 4.9, respectively, will be used to calculate summary statistics. An exception to this rule is any value reported as < 1 or < 0.1, etc. For values reported as < 1 or < 0.1, a value of 0.9 or 0.09, respectively, will be used to calculate summary statistics.
- A value that is 1 unit above the LOQ will be used to calculate descriptive statistics if the datum is reported in the form of “> x” (where x is considered the LOQ). Values with decimal points will follow the same logic as above.
- The LOQ will be used to calculate descriptive statistics if the datum is reported in the form of “≤ x” or “≥ x” (where x is considered the LOQ).

If methods based on the assumption that the data are normally distributed are not adequate, analyses may be performed on transformed data or nonparametric analysis methods may be used, as appropriate.

Sparse PK concentration values that are below the limit of quantitation (BLQ) will be presented as “BLQ” in the data listing.

3.8. Analysis Visit Windows

3.8.1. Definition of Baseline and Study Day

Baseline is defined as the last observation prior to the first dose of study drug, unless otherwise specified.

Study Day 1 is defined as the day of first dose of study drug. Study day will be calculated from the first dosing date of study drug and derived as follows:

- For post-dose study days: Assessment Date – First Dosing Date + 1
- For days prior to the first dose: Assessment Date – First Dosing Date

3.8.2. Analysis Visit Windows

The nominal visit as recorded on the CRF will be used when data are summarized by visit. Any data relating to unscheduled visits will not be assigned to a particular visit or time point.

However, the following exceptions will be made:

- An unscheduled visit prior to the first dosing of study drug may be included in the calculation of the baseline value, if applicable.
- Unscheduled visits after the first dosing of study drug will be included in determining the maximum postbaseline toxicity grade.
- The analysis window for Morphologic Leukemia-free State (MLFS) rate at Cycle 1 Day 14 is defined as Cycle 1 Day 1 + 13 (± 2) days.

3.8.3. Selection of Data in the Event of Multiple Records in an Analysis Visit Window

Depending on the statistical analysis method, single values may be required for each analysis window. For example, change from baseline by visit usually requires a single value, whereas a time-to-event analysis would not require 1 value per analysis window.

If multiple valid, nonmissing, continuous measurements exist in an analysis window, records will be chosen based on the following rules if a single value is needed:

- For baseline, if there are multiple measurements with the same time or no time recorded on the same day, the average of these measurements (for continuous data) will be used.
- For postbaseline values:
 - The record closest to the nominal day for that visit will be selected.
 - If there are 2 records that are equidistant from the nominal day, the later record will be selected.
 - If there is more than 1 record on the selected day, the average will be taken, unless otherwise specified.

If multiple valid, nonmissing, categorical measurements exist in an analysis window, records will be chosen based on the following rules if a single value is needed:

- For baseline, if there are multiple records with the same time or no time recorded on the same day, the value with the lowest severity will be selected (eg, normal will be selected over abnormal for safety electrocardiogram [ECG] findings).
- For postbaseline visits, if there are multiple records with the same time or no time recorded on the same day, the value with the worst severity within the window will be selected (eg, abnormal will be selected over normal for safety ECG findings).

4. SUBJECT DISPOSITION

4.1. Subject Enrollment and Disposition

A summary of subject enrollment will be provided by treatment group, phase, and dose level, treatment arm, or cohort if applicable, as elaborated in [Table 3-2](#) in Section 3.2, for each investigator within a country. The summary will present the number and percentage of subjects enrolled. For each column, the denominator for the percentage calculation will be the total number of subjects analyzed for that column.

A similar enrollment table will be provided by randomization stratum for Group B Phase 2 randomization. If there are discrepancies in the value used for stratification assignment between the IWRS and the clinical database, the value collected in the clinical database will be used for the summary. A listing of subjects with discrepancies in the value used for stratification assignment between the IWRS and the clinical database at the time of data finalization will be provided.

The randomization schedule used for Group B Phase 2 randomization will be provided as an appendix to the CSR.

A summary of subject disposition will be provided by treatment group, phase, and dose level, treatment arm, or cohort if applicable, as elaborated in [Table 3-2](#) in Section 3.2. This summary will present the number of subjects enrolled/randomized, and the number of subjects in each of the categories listed below:

- Full Analysis Set
- Safety Analysis Set
- Not Treated with ENTO
 - Treated with ENTO
 - Completed ENTO dosing as specified per protocol
 - Prematurely discontinued ENTO with reasons
- Not Treated with cytarabine (applicable to Group A only)
 - Treated with cytarabine (applicable to Group A only)
 - Completed cytarabine dosing as specified per protocol
 - Prematurely discontinued cytarabine with reasons

- Not Treated with daunorubicin (applicable to Group A only)
 - Treated with daunorubicin (applicable to Group A only)
 - Completed daunorubicin dosing as specified per protocol
 - Prematurely discontinued daunorubicin with reasons
- Not Treated with decitabine or azacitidine (applicable to Group B only)
 - Treated with decitabine or azacitidine (applicable to Group B only)
 - Completed decitabine or azacitidine dosing as specified per protocol
 - Prematurely discontinued decitabine or azacitidine with reasons
- Study Completion Status
 - Completed the protocol-planned duration of the study
 - Prematurely discontinued study with reasons

For the status of study drug and study completion and reasons for premature discontinuation, the number and percentage of subjects in each category will be provided. The denominator for the percentage calculation will be the total number of subjects in the All Enrolled Analysis Set or All Randomized Analysis Set corresponding to that column. A summary of subject disposition with all treatment groups combined will also be provided, presenting the number of subjects screened, the number of subjects enrolled/randomized, the number of subjects in the FAS, the number of subjects in the Safety Analysis Set, and the number of subjects in different study completion statuses. In addition, flowcharts will be provided to depict the disposition.

The following by-subject listings will be provided by subject identification (ID) number in ascending order to support the above summary tables:

- Reasons for discontinuing study treatment or study
- Reasons for screen failure (will be provided by screening ID number in ascending order)
- Lot number

Listings of ID numbers of the subjects who will be included in the pooled analyses of Group C will be provided.

4.2. Extent of Study Drug Exposure and Adherence

Extent of exposure to study drug will be examined by assessing the total duration of exposure to ENTO, the number of treatment cycles, the level of adherence to ENTO, and the number of doses of chemotherapy if applicable. The following analyses will be presented by treatment group, phase, and dose level, treatment arm, or cohort if applicable, as elaborated in [Table 3-2](#) in [Section 3.2](#). Summaries will be provided for the Safety Analysis Set.

4.2.1. Exposure to ENTO

Total duration of exposure to ENTO will be defined as (last dosing date of ENTO - first dosing date of ENTO + 1), regardless of temporary interruptions in ENTO administration, and will be expressed in weeks using up to 1 decimal place (eg, 4.5 weeks). If the last study drug dosing date is missing, the latest date among the study drug end date, clinical visit date, laboratory sample collection date, and vital signs assessment date that occurred during the on-treatment period will be used.

The total duration of exposure to ENTO will be summarized using descriptive statistics and using the number and percentage of subjects exposed for at least 1 day, 14 days, and 1, 2, 3, 6, 9, 12, and 15 months (if appropriate).

The number of induction cycles for Groups A and B and the number of cycles for Group C will be summarized using descriptive statistics. The number and percentage of subjects exposed to a given cycle category for induction therapy for Groups A and B, ENTO monotherapy for Group C, post-remission therapy for Group A Phase 2, and ENTO + Hypomethylating agent maintenance for Group B will be presented. The number and percentage of subjects who received ENTO monotherapy maintenance will also be summarized for Groups A and B.

The number and percentage of subjects who had dose reduction will be summarized.

4.2.2. Adherence to ENTO

The presumed total number of doses administered to a subject will be determined by the data collected on the drug accountability CRF using the following formula:

Total Number of Doses Administered =

$$\left(\sum \text{No. of Doses Dispensed} \right) - \left(\sum \text{No. of Doses Returned} \right)$$

The level of on-treatment adherence to the study drug regimen will be determined by the total amount of study drug administered relative to the total amount of study drug expected to be administered during a subject's actual on-treatment period based on the study drug regimen. Investigator-prescribed interruption and reductions as specified in the protocol will be taken into account. If there are treatment periods that bottles are not returned or the return information is missing, these periods will be excluded from the on-treatment adherence calculation for both total amount of study drug administered and study drug expected to be administered. If subjects never returned any bottle, the adherence will be set as missing.

The level of on-treatment adherence will be expressed as a percentage using the following formula:

$$\text{On-Treatment Adherence (\%)} = \left(\frac{\text{Total Amount of Study Drug Administered}}{\text{Study Drug Expected to be Administered on Treatment}} \right) \times 100$$

Descriptive statistics for the level of on-treatment adherence to ENTO with the number and percentage of subjects belonging to adherence categories (eg, < 75%, ≥ 75%) will be provided.

No formal statistical testing is planned.

By-subject listings of ENTO administration and accountability will be provided separately by subject ID number and visit (in chronological order).

4.2.3. Exposure to Chemotherapy

The exposure to each of the chemotherapies will be summarized by the number of doses received using descriptive statistics. The number and percentage of subjects for each distinct number of doses will be provided.

By-subject listings of chemotherapy administration will be provided.

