3.1.2. Group A Phase 2 (Dose Expansion): Entospletinib + cytarabine + daunorubicin (7+3)

Note: At the time of this amendment, Group A Phase 2 had completed enrollment.

Entospletinib lead-in (Cycle 0): ENTO 400 mg will be administered orally every 12 hours on Days 1-14 as a single agent during the lead-in (Cycle 0). However, cytarabine and daunorubicin (7+3) treatment (Cycle 1) may be started earlier, after 5 days of exposure to ENTO, if the Principal Investigator agreed with the treating physician that treatment should start sooner. Examples of such situations may include but are not limited to:

- White blood cell count is increasing and greater than 20,000/ μ L
- Leukemic related complications that in the opinion of the treating physician require the initiation of cytotoxic chemotherapy sooner

Hydroxyurea is allowed during the lead-in period per investigator discretion and after discussion with the medical monitor. Hydroxyurea should be discontinued prior to initiating cytarabine and daunorubicin (7+3) chemotherapy.

A bone marrow aspirate for disease assessment will be performed at the end of the monotherapy lead-in period (ie, Cycle 0 Day 14 or after the minimum 5 days of ENTO), and prior to initiating induction chemotherapy.

Subjects with cytogenetic and molecular mutations at screening must have cytogenetic and molecular mutation testing repeated at subsequent bone marrow examinations (Cycle 0 Day 14, Cycle 1 Day 14, count recovery, End of Study).

ENTO 400 mg will continue to be given every 12 hours from Cycle 0 Day 1 to the completion of induction therapy as determined by bone marrow response.

Entospletinib + 7+3 (Cycle 1-2): ENTO 400 mg will be administered every 12 hours in combination with IV cytarabine (Days 1-7) and IV daunorubicin (Days 1-3) for up to 2 induction cycles (Cycle 1 and 2). Subjects must be able to receive 2 cycles of induction chemotherapy.

A bone marrow aspirate and biopsy will be performed on Cycle 1 Day 14. If the bone marrow cellularity at this time point is $\leq 20\%$, a repeat bone marrow examination will occur within 2 weeks or at count recovery, whichever came first. Subjects with residual disease detected at the Cycle 1 Day 14 bone marrow evaluation will proceed with Cycle 2 of induction chemotherapy. The start of Cycle 2 will depend on the timing and result of the disease assessment. Subjects will continue receiving ENTO while awaiting disease assessment results.

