The investigator must consult the medical monitor if subjects have not obtained a CR after Cycle 1 and prior to Cycle 2, and if there is any consideration to omit Cycle 2 of induction chemotherapy.

Subjects with cytogenetic and molecular mutations at screening must have cytogenetic and molecular mutation testing repeated at subsequent bone marrow examinations (Cycle 0 Day 14, Cycle 1 Day 14, count recovery, End of Study).

Subjects will undergo a daily CBC from Cycle 1 Day 14 (ie, count nadir) until count recovery at which time a bone marrow aspirate and biopsy will be performed.

Once a CR/CRi is confirmed on a recovery bone marrow examination (ie, the subject achieves < 5% blasts by morphology and flow cytometry), the subject will proceed to either allogeneic stem cell transplantation (SCT) or post-remission chemotherapy with cytarabine.

If CR/CRi is not achieved by the end of Cycle 2, the subject will be considered a treatment failure and will have met study efficacy endpoint criteria, but will remain on study for required study-related follow-up procedures.

Entospletinib + cytarabine post-remission (at least 3 cycles, and up to 4 cycles):

Post-remission chemotherapy will be offered to eligible subjects who have achieved CR/CRi and do not require or cannot proceed to allogeneic SCT. In addition, subjects who are awaiting a donor or transitioning to allogeneic SCT will be allowed to receive post-remission chemotherapy per investigator discretion. Therapy will consist of 3g/m² high dose cytarabine administered IV every 12 hours on Days 1, 3, and 5 (< 60 years of age) or 1g/m² cytarabine administered once daily on Days 1-5 (≥ 60 years of age) in combination with 400 mg ENTO every 12 hours on Days 1-28 of each 28-day cycle.

[figure not shown]
Subjects in whom definitive post-remission chemotherapy is planned will receive at least 3 and up to 4 cycles of cytarabine. Subjects who are awaiting a donor or transitioning to SCT may receive at least 1 and up to 4 cycles of cytarabine.

A bone marrow aspirate sample will be collected for disease assessment and biomarker research at the end of every 2 cycles (Cycle 2 Day 28 and Cycle 4 Day 28) and at suspected disease progression. Subjects who continue to maintain a CR/CRi after 3-4 cycles of post-remission chemotherapy will be offered maintenance with ENTO 400 mg every 12 hours for up to 12 cycles.

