It is recognized that drug-related hematologic toxicity in this population may be difficult to ascertain given the aggressive hematologic disease and the fact that multiple cycles of therapy may need to be administered for maximal clinical response. Therefore, there will be no dose modifications for hematologic toxicity due to ENTO, decitabine or azacitidine during the first 3 cycles for subjects with active AML. However, after the third cycle of ENTO and decitabine is administered, subjects suspected to have study treatment related ANC and/or platelet count toxicity (ie, fail to recover to at least 50% of the prior cycle's baseline value) will have the dose of decitabine reduced to 20 mg/m²/d on Days 1-9 and the dose of ENTO reduced one dose level. Similarly, after the third cycle of ENTO and azacitidine administration, subjects suspected to have study treatment related ANC and/or platelet count toxicity (ie, fail to recover to at least 50% of the prior cycle's baseline value) will have the dose of azacitidine reduced according to [Table 3-7](#) and the dose of ENTO reduced one dose level. Dose modifications because of concern for drug induced cytopenias prior to Cycle 4 will be discussed with the medical monitor. Dose modifications for hematologic toxicity for subjects who have achieved a CR or CRi are detailed below. For additional safety information, reference the package insert for decitabine and azacitidine.

Table 3-7. Azacitidine Dose Modifications

Nadir Counts		% Dose in the Next Course
ANC (x10⁹/L)	Platelets (x10⁹/L)	
< 0.5	< 25.0	50%
0.5 –1.5	25.0-50.0	67%
> 1.5	> 50.0	100%

Dose Modifications for Hematologic Toxicity for Subjects Who HAVE Achieved < 5% Blasts and Receive Maintenance Therapy With Decitabine or Azacitidine

Subjects who have had a previous dose reduction of decitabine and ENTO and then subsequently have a decrease in blasts to < 5% by morphology, the number of days of decitabine will be reduced to Days 1-4 of each cycle, but the daily dose will remain the same. For example, a subject receiving 20 mg/m²/day on Days 1-9 will move on to receive 20 mg/m²/day on Days 1-4. Subjects will receive the same dose reduction of ENTO. For azacitidine, no dose reduction regimen is necessary.

Neutropenia

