WBC or Platelet Nadir % decrease in counts from baseline	Bone Marrow Biopsy Cellularity at Time of Nadir (%)		
	30-60	15-30	<15
	% Dose in the Next Course		
50 - 75	100	50	33
>75	75	50	33

Dose Modifications for Non-hematologic Toxicity for Subjects Who HAVE Achieved CR or CRi and Receive Maintenance Therapy With Decitabine or Azacitidine

Subjects who experience any significant Grade 3 or greater toxicity attributed to decitabine, azacitidine, or ENTO will hold the protocol therapy until it resolves to \leq Grade 2. Then restart ENTO with one dose level reduction and reduce the dose of decitabine to 20 mg/m²/d on Days 1-4 for the first occurrence and decrease the dose of decitabine to 20 mg/m²/d on Days 1-3 for the second occurrence and restart ENTO at the next lower dose. For azacitidine specifically, 50% dose reduction will be applied in combination with ENTO at the next lower dose. Subjects who require a dose reduction below dose level -1 will not receive ENTO and instead will continue maintenance with decitabine or azacitidine alone. If the toxicity recurs for a third time during treatment period, therapy should be discontinued. Decitabine/ENTO or azacitidine/ENTO should not be restarted until the toxicity has resolved to Grade 2 or better. Subjects with controlled Grade 3 infection or febrile neutropenia may continue decitabine or azacitidine in combination with ENTO. If a subject experiences pneumonitis at Grade 4, study treatment must be discontinued but may continue with decitabine or azacitidine alone.

Dose reductions (for either hematologic or non-hematologic toxicity) for subjects with < 5% blasts by morphology may be done twice during the course of maintenance therapy, if necessary.

Group C:

Dose modifications and delays attributed to ENTO for hematologic and non-hematologic toxicities will follow the guidelines in [Appendix 3](#).

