8.6.1. Extent of Exposure

Descriptive information will be provided by dose level regarding the number of doses of study therapy prescribed, the total number of doses taken, the percent of expected doses taken, duration of treatment, and the number and timing of prescribed dose reductions and interruptions.

ENTO compliance will be described in terms of the proportion of study treatment actually taken based on returned pill count relative to the amount that was dispensed (taking into account physician-prescribed reductions and interruptions).

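### SAP 4.2.3 summarises chemotherapy exposure only as a dose count, which cannot show percent-of-dose reductions and pools cytarabine doses of very different size

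*SAP*

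**What the plan says.** SAP 4.2 lists the exposure measures. Chemotherapy enters only at the end: "the level of adherence to ENTO, and the number of doses of chemotherapy if applicable". SAP 4.2.3 repeats this ("The exposure to each of the chemotherapies will be summarized by the number of doses received using descriptive statistics"), adds the distribution of distinct dose numbers, and then states: "By-subject listings of chemotherapy administration will be provided". The adherence percentage (SAP 4.2.2) and the count of subjects with a dose reduction (SAP 4.2.1) stand under ENTO headings.

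Protocol 8.6.1 plans, for study therapy, doses prescribed and taken together with "the percent of expected doses taken, duration of treatment, and the number and timing of prescribed dose reductions and interruptions". Drug administration and exposure is a secondary endpoint in Protocol 2.2. SAP 7.7 declares one change from the protocol's safety analyses, and it is not this one.

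Protocol 3.3 reduces the two hypomethylating agents in different ways. For decitabine in maintenance after an earlier reduction, "the number of days of decitabine will be reduced to Days 1-4 of each cycle, but the daily dose will remain the same". For non-hematologic toxicity in maintenance, "For azacitidine specifically, 50% dose reduction will be applied in combination with ENTO at the next lower dose". Tables 3-7 and 3-8 also express azacitidine reductions as a percentage of dose.

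**The concern.** A dose count measures exposure only if doses are of similar size and reductions are made by leaving doses out. Neither condition holds for every agent here.

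In the randomised Group B cohort the two arms stand side by side in SAP Table 3-2. A reduction made by percentage leaves the azacitidine count unchanged, while a reduction made by days lowers the decitabine count. In Group A Phase 2, where SAP Table 3-2 has a single column, one cytarabine count covers induction and two age-dependent post-remission regimens.

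At stake is whether the exposure tables can support the safety reading of the combinations, which is a primary objective.

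**Working it through.** The plan states no cumulative dose or dose intensity, so there is no figure to reproduce. The check uses the protocol's schedules:

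- doses per cycle = days × doses per day
- amount per cycle = doses × dose per administration × fraction of full dose

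**Group B.** Inputs: decitabine 20 mg/m2 on 10 days (induction) or 5 days (maintenance), azacitidine 75 mg/m2 on 7 days (Protocol Tables 3-3 and 3-4); reductions from Protocol 3.3. I assume a percentage reduction applies to each daily dose and all seven days are given.

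| Agent and level | Doses per cycle | mg/m2 per cycle | Count ratio | Amount ratio |
|---|---|---|---|---|
| Azacitidine, full | 7 | 7 × 75 = 525 | 1.00 | 1.00 |
| Azacitidine, 75% | 7 | 393.75 | 1.00 | 0.75 |
| Azacitidine, 67% | 7 | 351.75 | 1.00 | 0.67 |
| Azacitidine, 50% | 7 | 262.5 | 1.00 | 0.50 |
| Azacitidine, 33% | 7 | 173.25 | 1.00 | 0.33 |
| Decitabine induction, 10 to 9 days | 9 | 180 of 200 | 0.90 | 0.90 |
| Decitabine maintenance, 5 to 4 days | 4 | 80 of 100 | 0.80 | 0.80 |
| Decitabine maintenance, 5 to 3 days | 3 | 60 of 100 | 0.60 | 0.60 |

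Take four induction cycles with a reduction in the fourth. Decitabine gives 39 of 40 doses and 780/800 = 97.5% of the amount. Azacitidine at 50% gives 28 of 28 doses and (3 × 525 + 262.5)/2100 = 87.5%. The larger loss is the one that the count misses.

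A lower decitabine count still does not identify a reduction. A total of 39 fits 10 + 10 + 10 + 9, and equally three full induction cycles plus three maintenance cycles of three days (30 + 9).

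**Group A cytarabine.** Induction is given "in combination with IV cytarabine (Days 1-7) and IV daunorubicin (Days 1-3) for up to 2 induction cycles" at 100 mg/m2 (Protocol Table 3-1), read as per 24 hours in line with the renal-dosing text of Protocol 3.3. Post-remission doses are from Protocol 3.1.2. Per cycle, with one counted dose per induction day:

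- induction: 7 doses, 7 × 0.1 = 0.7 g/m2
- post-remission, under 60: 6 doses, 6 × 3 = 18 g/m2
- post-remission, 60 and over: 5 doses, 5 × 1 = 5 g/m2

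One induction plus three post-remission cycles:

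- under 60: 7 + 18 = 25 doses; 0.7 + 54 = 54.7 g/m2
- 60 and over: 7 + 15 = 22 doses; 0.7 + 15 = 15.7 g/m2

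The count ratio is 25/22 = 1.14 and the amount ratio 54.7/15.7 = 3.5. The order is the same, but the gap is heavily compressed.

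Inversions do occur. Two induction cycles alone give 14 doses and 1.4 g/m2. One induction plus one under-60 post-remission cycle gives 13 doses and 18.7 g/m2. I listed all 18 planned paths (1 or 2 induction cycles, 0 to 4 post-remission cycles, two age groups) and compared every pair, unweighted. Of 153 pairs, 123 keep the same order, 29 are reversed (19%) and 1 is tied on count.

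If an induction course is instead recorded as one infusion, 132 pairs agree, 20 are reversed and 1 is tied, and the per-cycle order (1 < 5 < 6 doses) matches the amount. SAP 4.2.3 does not say which convention applies.

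**Renal reductions of high-dose cytarabine** (Protocol 3.3, 60% or 50%): 18 g/m2 becomes 10.8 or 9.0 with 6 doses still counted; 5 g/m2 becomes 3.0 or 2.5 with 5 doses still counted.

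**The case against.** The case on the other side has real weight.

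- **Other outputs carry chemotherapy information.** SAP 4.1 reports completion or premature discontinuation of each agent. SAP 4.2.1 tabulates cycle categories for induction, post-remission and hypomethylating-agent maintenance. SAP 7.1.6.1 counts subjects with a treatment-emergent event leading to chemotherapy reduction or interruption. Administration is listed by subject. This stands, so nothing is lost from the report as a whole. But the adverse-event line merges reduction with interruption, gives neither size nor timing, and need not capture a cytarabine reduction set by renal function. A listing is not a summary.
- **Protocol 8.6.1 works in doses, not mg/m2, and may mean ENTO.** It reports by dose level, moves on to ENTO pill counts, and Protocol 8.2.1 ties study treatment to ENTO. That reading is possible. Against it, SAP 7.1.3 cites case report form questions that name each chemotherapy agent as study treatment. A cumulative dose in mg/m2 is therefore a better measure, not something the protocol promised.
- **The decitabine rule is not uniform.** For non-hematologic toxicity during induction, Protocol 3.3 sends both agents to their package inserts. The contrast between arms holds for the reductions that the protocol itself spells out.
- **Little depends on it.** The analysis is descriptive, and SAP Section 1 records that Group B Phase 2 closed before its planned size. This stands and sets the severity.

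A reader might infer that the count ranks cytarabine exposure in reverse. It does not in general: the two post-remission regimens keep their order per cycle, and most pairs of paths agree. A reader might also infer that the tables would show reductions on the decitabine arm and none on the azacitidine arm. Without an expected number, neither arm's reductions can be identified from a total.

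**Conclusion.** The point holds as a minor one. As written, the chemotherapy exposure summary does not register azacitidine reductions to 33–75% of dose or renal reductions of high-dose cytarabine, whereas day-based decitabine reductions move the count. In Group A Phase 2 it renders a 3.5-fold difference in cytarabine amount as a 14% difference in doses. No other planned summary supplies the amount received or the size and timing of reductions.

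This rests on three assumptions: one counted dose per induction day for the cytarabine figures, percentage reductions applied to each azacitidine dose, and full planned schedules otherwise. How often reductions occurred cannot be known from the documents.

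If study therapy in Protocol 8.6.1 includes chemotherapy, the percentage of expected doses and the number and timing of reductions and interruptions were also dropped without a declaration in SAP 7.7. If it means ENTO alone, that part falls away and the measurement problem remains. No test, error rate or sample size is affected.

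**What to change.** In SAP 4.2.3:

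1. Define a counted dose, in particular whether a cytarabine induction course is one infusion or one dose per day.
2. For each agent, report the percent of protocol-planned dose received and the cumulative dose in mg/m2, and define the planned dose used as denominator (for example, the full protocol dose for each cycle started).
3. Split by treatment period: induction, post-remission by regimen, and hypomethylating-agent maintenance.
4. Add the number of subjects with a dose reduction or an omitted day, with timing by cycle.
5. Keep the dose count as a supplementary line.

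State in SAP 7.7 how Protocol 8.6.1 is read for chemotherapy, and declare anything left out.

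The cost is SAP wording and one or two descriptive tables. This assumes the chemotherapy administration records hold the amount given; the case report form is not among the documents. If only dates were recorded, the tables should say that amounts are unavailable and report omitted days.
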